### **13.6. Quality Assurance and Quality Control**

Each trial site shall be required to have Standard Operating Procedures (SOP's) to define and ensure quality assurance/control processes for trial conduct, data generation & collection, recording of data/documentation and reporting according to the protocol, GCP and any applicable local, national or international regulations.

### **13.7. Disclosure and Publication Policy**

All information provided regarding the trial, as well as all information collected/documented during the course of the trial, will be regarded as confidential. The Sponsor reserves the right to release literature publications based on the results of the trial. Results from the trial will be published/presented as per the Sponsor's publication strategy.

The financial disclosure information will be provided to the Sponsor prior to trial participation from all PIs and Sub-Investigators who are involved in the trial and named on the FDA 1572 form.

## 15. APPENDICES

## Appendix 1: ECOG Performance Status Criteria

ECOG Performance Status Scale		Karnofsky Performance Scale	
Grade	Descriptions	Percent	Description
0	Normal activity. Fully active, able to carry on all pre-disease performance without restriction.	100	Normal, no complaints, no evidence of disease.
		90	Able to carry on normal activity; minor signs or symptoms of disease.
1	Symptoms, but ambulatory. Restricted in physically strenuous activity, but ambulatory and able to carry out work of a light or sedentary nature (e.g., light housework, office work).	80	Normal activity with effort; some signs or symptoms of disease.
		70	Cares for self, unable to carry on normal activity or to do active work.
2	In bed <50% of the time. Ambulatory and capable of all self-care, but unable to carry out any work activities. Up and about more than 50% of waking hours.	60	Requires occasional assistance, but is able to care for most of his/her needs.
		50	Requires considerable assistance and frequent medical care.
3	In bed >50% of the time. Capable of only limited self-care, confined to bed or chair more than 50% of waking hours.	40	Disabled, requires special care and assistance
		30	Severely disabled, hospitalization indicated. Death no imminent.
4	100% bedridden. Completely disabled. Cannot carry on any self-care. Totally confined to bed or chair.	20	Very sick, hospitalization indicated. Death not imminent.
		10	Moribund, fatal processes progressing rapidly.
5	Dead	0	Dead

## Appendix 2: Diagnostic Criteria and Staging for Multiple Myeloma

### International Myeloma Working Group Criteria for Diagnosis

The following criteria must be met except as noted:

- clonal bone marrow plasma cells  $\geq 10\%$
- presence of serum and/or urinary monoclonal protein (except in patients with non-secretory multiple myeloma\*) and
- evidence of end-organ damage, which can be attributed to the underlying plasma cell proliferative disorder, specifically:
  - hypercalcemia: serum calcium  $\geq 11.5$  mg/dL
  - renal insufficiency: serum creatinine  $> 2$  mg/dL
  - anemia: normochromic, normocytic with a hemoglobin value of  $> 2$  g/dL below the lower limit of normal or, a hemoglobin value of  $< 10$  g/dL
  - bone lesions: lytic lesions, severe osteopenia or pathologic fractures

\*More than 10% clonal plasma cells are required for the diagnosis of nonsecretory myeloma

Dimopoulos, et al., Consensus recommendations for standard investigative workup: report of the International Myeloma Workshop Consensus Panel 3. 2011 Blood J 117: 4701-4705

#### A. Durie and Salmon Staging System

##### Stage I

All of the following:

- Hemoglobin  $> 10$  g/dL
- Serum calcium  $< 12$  mg/dL
- Normal bone structure or solitary plasmacytoma on radiographs
- Low M component
  - IgG  $< 5$  g/dL
  - IgA  $< 3$  g/dL
  - Urine light chains  $< 4$  g/24 hours

##### Stage II

Fitting neither Stage I nor Stage III

### Stage III

One or more of the following:

- Hemoglobin < 8.5 g/dL
- Serum calcium >12 mg/dL
- Advanced lytic bone lesions
- Hyper M component
  - IgG > 7 g/dL
  - IgA > 5 g/dL
  - Urinary light-chain excretion > 12 g/24 hour

### Subclassification

A: serum creatinine < 2.0 mg/dL

B: serum creatinine equal to or > 2.0 mg/dL

## B. International Staging System (ISS) for Myeloma

**Stage I**      Serum  $\beta_2$ -microglobulin < 3.5 mg/L  
                  Serum albumin  $\geq$  3.5 g/dL

---

**Stage II**      Fitting neither Stage I nor III\*

---

**Stage III**     Serum  $\beta_2$ -microglobulin  $\geq$  5.5 mg/L

\*There are two categories for stage II: serum  $\beta_2$ -microglobulin < 3.5 mg/L but serum albumin < 3.5 g/dL; or serum  $\beta_2$ -microglobulin  $\geq$  3.5 mg/L and < 5.5 mg/L irrespective of the serum albumin level.

Greipp P., et al., International staging system for multiple myeloma. 2005. JCO 23:3412-3420

### Appendix 3: International Myeloma Working Group Uniform Response Criteriaa

Response Category	Definition

sCR Stringent Complete Response
	
CR criteria as defined below AND
 
 
• Normal free light chain (FLC) ratio
 
 
AND
 
 
• Absence of clonal PCs by immunohistochemistry or 2-to 4-color flow cytometry
 

CR Complete Response
	
 
• Negative immunofixation on the serum and urine
 
 
AND
 
 
• Disappearance of any soft tissue plasmacytoma(s)
 
 
AND
 
 
• <math>\leq 5\%</math> plasma cells in bone marrowb.
 
• In case the only measurable disease in a patient with CR at baseline is the serum FLC level, a normal FLC ratio of 0.26 to 1.65 is required additionally to qualify for CR.
 

VGPR Very Good Partial Response
	
 
• Serum and urine M-protein detectable by immunofixation but not by electrophoresis (PEP) or <math>\geq 90\%</math> reduction from baseline serum) AND urine M-protein level <math>< 100</math> mg/ 24h
 
 
AND
 
 
• In case of presence of soft tissue plasmacytoma(s) at baseline, disappearance of any soft tissue plasmacytomas
 
 
In case the only measurable disease in a patient with VGPR at baseline is the serum FLC level (i.e. no measurable disease in serum and urine PEP), a decrease of <math>> 90\%</math> in the difference between involved and uninvolved FLC levels from baseline is required.


PR Partial Response
	
<math>\geq 50\%</math> reduction from baseline in serum M-protein
 
AND
 
<math>\geq 90\%</math> reduction from baseline in 24h urinary M-protein OR urine M-protein <math>< 200</math> mg/24h
 
If serum and urine M-protein are non-measurable at baseline, a <math>\geq 50\%</math> reduction from baseline in the difference between involved and uninvolved FLC levels is required in place of the M-protein criteria.
 
If serum and urine M-protein are non-measurable, and serum free light assay is also non-measurable, <math>\geq 50\%</math> reduction from baseline in percent plasma cells in bone marrow is required instead of M-protein measurement, provided baseline plasma cells in bone marrow was <math>\geq 30\%</math>.
 
AND
 
In case of presence of soft tissue plasmacytoma(s) at baseline, a reduction in the SPD by <math>\geq 50\%</math> is required.

**Appendix C: International Myeloma Working Group Uniform Response Criteria: Complete Response and Other Response Categories (continuation)**

SD	Not meeting criteria for sCR, CR, VGPR, PR or PD
PDc Progressive Disease	
Increase of <math>\geq 25\%</math> from the nadir in at least one of the following criteria:
 
 
• serum M-protein (absolute increase must be <math>\geq 0.5</math> g/dL)
 
• urine M-protein (absolute increase must be <math>\geq 200</math> mg/24h)
 
• only in patients with non-measurable serum and urine M-protein levels: difference in involved and uninvolved FLC levels (absolute increase must be <math>>10</math> mg/dL)
 
• only in patients with non-measurable serum and urine M-protein levels and non-measurable disease by FLC levels, bone marrow plasma cell percentage (absolute % must be <math>\geq 10\%</math>)
 
 
OR
 
 
• definite development of new lytic bone lesions or increase from baseline in size of lytic bone lesion(s)
 
 
OR
 
 
• development of new soft tissue plasmacytoma(s) or definite increase from nadir in existing soft tissue plasmacytomas
 
 
OR
 
 
• development of hypercalcemia (corrected serum calcium <math>>11.5</math> mg/dL) for patients without hypercalcemia at baseline. In case of preexisting hypercalcemia at baseline, PD will only be assessed due to the hypercalcemia criterion in case the corrected serum calcium level was <math>\leq 11.5</math> mg/dL post-baseline and increased thereafter beyond 11.5 mg/dL.
 

Patients with relapsed refractory myeloma (adopted from the European Group for Blood and Marrow Transplantation [EBMT] criteria)	
MR Minimal Response	
 
• <math>\geq 25\%</math> but <math>\leq 49\%</math> reduction of serum M protein and reduction in 24-hour urine M-protein by 50-89%
 
 
AND
 
 
• If present at baseline, 25-49% reduction in the size of soft tissue plasmacytomas is also required
 
• No increase in size or number of lytic bone lesions (development of compression fracture does not exclude response)
 

aAll response categories require two consecutive assessments made at any time before the institution of any new therapy; all categories also require no known evidence of progressive or new bone lesions if radiographic studies were performed. Radiographic studies are not required to satisfy these response requirements.

bConfirmation with repeat bone marrow biopsy not needed.

cAt any point in this treatment, patients suspected of PD will have response assessed again to confirm disease progression (i.e. 2 sets of response assessments at least 1 week apart). The outcomes will be reviewed by the study chair before the patient is removed from the study

Rajkumar et al. Consensus recommendations for the uniform reporting of clinical trials: report of the International Myeloma Workshop Consensus Panel 1. Blood J 2011 117: 4691-4695

Blade J, Samson D, Reece D, et al. Criteria for evaluating disease response and progression in patients with multiple myeloma treated by high dose therapy and haemopoietic stem cell transplantation:

Myeloma Subcommittee of the EBMT, European Group for Blood and Marrow Transplant. *Br J Haematol.* 1998;102(5):1115-1123.

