#### 1.3.1. Carfilzomib Phase 2 Single Agent Experience

Two Phase 2 clinical studies are ongoing with carfilzomib in multiple myeloma (MM) patients, PX-171-003-A0 (N=46) in relapsed and refractory MM and PX-171-004 (N=39) in relapsed MM. In both studies, patients were treated with 20 mg/m^2 on Days 1, 2, 8, 9, 15, and 16 every 28 days. In these studies there were four cases of suspected or documented tumor lysis syndrome (TLS) prior to institution of the prophylaxis guidelines. Since these guidelines were implemented, no further cases of TLS have been reported. In both studies, the most common adverse events were fatigue, anemia, thrombocytopenia, gastrointestinal, and dyspnea. There were reported cases of increased in serum creatinine that were primarily < Grade 2. A very low rate of treatment-emergent peripheral neuropathy ( 2.2% Grade 3/4), was observed in PX-171-003-A0 despite the fact that 78% of patients had Grade 1/2 neuropathy upon study entry (Jagannath et al. 2009).

Patients in the PX-171-003-A0 study had progressive myeloma and were refractory to their most recent therapy, often including bortezomib and/or an immunomodulatory drug

(usually lenalidomide). In this study, 18% of patients had partial responses, with 7% minor responses and 41% stable disease. The median time to progression on the PX-171-003-A0 study was 5.1 months with duration of response of 7.4 months (Jagannath et al. 2009).

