## 9. RESPONSE EVALUATIONS AND MEASUREMENTS

Response to treatment and disease progression will be evaluated using the International Myeloma Working group Uniform Response Criteria: Disease Progression and Relapse (see Appendix C).

CR	Complete Response
sCR	subcategory: stringent complete response
VGPR	Very good partial response
PR	Partial response
SD	Stable disease
PD	Progressive disease

All response categories (CR, sCR, VGPR, PR, PD) require two consecutive assessments made at any time before the institution of any new therapy, as well as no known evidence of progressive or new bone lesions if radiographic studies were performed. Radiographic studies are not required to satisfy these response requirements. Bone marrow assessments are not required to be confirmed by repeat testing.

Complete Response should be confirmed with a bone marrow biopsy for morphology and a bone marrow aspiration for flow cytometry, FISH and cytogenetics performed locally. Additional confirmatory studies include SPEP, UPEP, immunofixation of blood and urine and serum free light chains (see Appendix E).

MR	Minimal Response
-----------	------------------

Minimal Response (MR) should be reported for patients with relapsed refractory myeloma. When reported, the specific rate of MR should be distinguished from PR or better.

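### Upper limits in the minimal response row push some deeper responders down to stable disease, and the stable disease row does not exclude minimal response (minor; secondary reporting only)

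*Combined protocol and SAP*

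**What the plan says.** The response table is Appendix 3 (cited elsewhere in the protocol as Appendix C). Four parts of it matter here.

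- **MR row**, adopted from the EBMT criteria. Serum M-protein must fall by at least 25% but no more than 49%, and there must be "reduction in 24-hour urine M-protein by 50-89" percent. For plasmacytomas: "If present at baseline, 25-49% reduction in the size of soft tissue plasmacytomas is also required". All three limbs have a floor and a ceiling.
- **PR row.** Serum must fall by at least 50%, and the urine condition must also be met. That condition is an either/or, "reduction from baseline in 24h urinary M-protein OR urine M-protein", with limits of at least 90% for the fall and below 200 mg/24h for the level.
- **SD row**, a residual: "Not meeting criteria for sCR, CR, VGPR, PR or PD". MR is not in the list.
- **Footnote a**: "All response categories require two consecutive assessments made at any time before the institution of any new therapy".

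Section 9 says MR should be reported in relapsed refractory myeloma and that "the specific rate of MR should be distinguished from PR or better". It gives no rule separating MR from SD and no order of assignment. Its own list of categories needing two consecutive assessments is CR, sCR, VGPR, PR and PD, which leaves out MR and SD. Section 10.4.1 builds the primary endpoint from CR, VGPR and PR only.

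**The concern.** An ordered response scale should never give a patient a worse category for a deeper fall. Here it can. The MR ceilings make sense only if every patient who passes one of them lands in PR. PR needs both serum and urine conditions, so a patient whose two markers respond unequally can be too good for MR and not good enough for PR. The only row left is SD.

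The second defect is independent of the first. Because SD is whatever is not sCR, CR, VGPR, PR or PD, an MR patient satisfies two rows at once. Two analysts working from the same data could report different SD rates, and both could point to the text.

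At stake is the MR rate that Section 9 asks for, and any SD rate tabulated beside it.

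**Working it through.** **Does the plan's own figure depend on this?** Section 10.1 gives 27 patients for 18% versus 36%, one-sided alpha 0.10, 80% power. An exact one-sample binomial test with n = 27 and success at 8 or more responders has alpha 0.098 and power 0.812, so the figure reproduces. It uses neither the MR row nor the SD row and does not change.

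**Applying the rows literally.** Both markers measurable, no plasmacytoma, no progression. Baseline serum 3.0 g/dL and urine 2000 mg/24h are illustrative.

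| Patient | Serum | Urine | PR? | MR? | Rows met |
|---|---|---|---|---|---|
| A | 3.0 to 1.8 (−40%) | 2000 to 800 (−60%) | No: serum below 50% | Yes | MR and SD |
| B | 3.0 to 0.9 (−70%) | 2000 to 800 (−60%) | No: urine below 90% and level not under 200 | No: serum above 49% | SD |
| C | 3.0 to 1.8 (−40%) | 2000 to 100 (−95%) | No: serum below 50% | No: urine above 89% | SD |
| D | 3.0 to 0.9 (−70%) | 2000 to 100 (−95%) | Yes | – | PR |

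B and C each do at least as well as A on both markers and better on one, yet rank below A. D shows the limit of the problem: a fall that meets both PR conditions is still PR. A shows the double label.

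**How much of the range is affected.** Take whole-percent falls that meet both MR floors: serum 25 to 100 (76 values) by urine 50 to 100 (51 values), so 76 × 51 = 3876 cells. The MR band is 25 × 40 = 1000 cells, and all 1000 also meet SD.

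- Baseline urine 2000 mg/24h: PR takes serum 50 to 100 by urine 90 to 100, 51 × 11 = 561 cells. Left: 3876 − 561 = 3315. Outside the MR band: 3315 − 1000 = 2315, or 70%.
- Baseline urine 300 mg/24h: any urine fall of 50% or more leaves a level below 200, so PR takes every cell with serum at 50% or more. Left: 25 × 51 = 1275. Outside the MR band: 275, or 22%.

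These are shares of cells, not of patients. They show that the gap depends on baseline urine, through the 200 mg/24h alternative in PR.

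**Shares of patients, under assumptions.** The documents give no distribution of falls, so every input here is assumed: serum and urine log-ratios bivariate normal, correlation 0.5 to 0.9, serum SD 0.6 or 0.9, urine SD 1.4 times that, mean −0.1 or −0.3, baseline urine lognormal and at least 200 mg/24h. Among patients who clear both MR floors without reaching PR, the share outside the ceilings is:

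- 47% to 69% with median baseline urine 1000 mg/24h (log-SD 0.7 or 1.0);
- 32% to 55% with median 300 to 400 mg/24h (log-SD 1.0). A narrower spread of baseline urine lowers this further.

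Reading the ceilings as below 50% and below 90% gives 44% to 67% at a median of 1000, so the gap is not a rounding effect. Counted over all dual-measurable patients, the misplaced group is about 5% to 17% at a median of 1000 and 3% to 10% at 300 to 400 (urine SD 1.0 or 1.4 times serum).

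**The case against.** The strongest reply is that nothing planned rests on these rows. The efficacy endpoints in Section 10.4 are overall response rate, TTP, PFS and OS. Response rate stops at PR, progression has its own row, and no section asks for an SD rate or a best-response table. Section 9 says MR should be reported and then hedges with when reported. All of this stands, and it makes the point minor. It does not make the rows consistent.

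A second reply is that any analyst would assign the best category met, which removes the double label. That is probably what would happen, but the protocol does not say so, and it would not close the ceiling gap.

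A third is that the MR wording is adopted from published criteria. That explains the ceilings. Setting that row beside an SD row that takes no account of it is still this protocol's choice.

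A reader might go further and infer that the trial's MR and SD rates can no longer be set against the single-agent carfilzomib results in Section 1.3.1, where "18% of patients had partial responses, with 7% minor responses and 41% stable disease", and that counting MR inside SD would turn 41% into 41 + 7 = 48%. The documents do not support this. Section 1.3.1 does not give the MR definition used in that study. If it used the same banded definition, moving to floors would create a mismatch rather than cure one. The 48% only adds two of that study's rates; nothing in this protocol directs such a tabulation.

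**Conclusion.** The point holds as a minor defect in secondary reporting. Two statements follow from the text alone. A dual-measurable patient who exceeds one MR ceiling without meeting both PR conditions is SD, and every MR patient also meets SD. The MR rate is therefore understated relative to a floor-based reading, and any SD rate takes in MR and better-than-MR patients. Overall response rate, TTP, PFS, OS and the sample size are unaffected.

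The size cannot be derived from the documents. Roughly one third to two thirds of dual-measurable patients between the MR floors and PR is an assumption-based range that falls with lower baseline urine. It should not be read as a share of the trial: inclusion criterion 2 requires only one measurable marker, and the number measurable in both fluids is unknown.

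There is a related gap. The MR row joins its serum and urine limbs and has no provision for patients measurable in serum only or by free light chains only, whom criterion 2 admits.

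**What to change.** 1. **MR row.** Replace the bands with floors: serum fall of 25% or more and 24-hour urine fall of 50% or more, with plasmacytomas, if present, reduced by 25% or more, and the patient not meeting PR or better. Apply each limb only to markers measurable at baseline, and state how patients measurable only by free light chains are handled.
2. **SD row.** Add MR to the categories that SD excludes.
3. **Order.** State that each patient is assigned the best category met.
4. **Confirmation.** Make Section 9's list of categories needing two assessments agree with footnote a. At present the footnote covers all categories and the list omits MR and SD.
5. **Knock-on wording.** The Synopsis, Section 5 and Section 5.2.2 continue patients with objective response or stable disease; Section 5.1.2 refers to stable disease or better. Once SD excludes MR, MR patients may fall in neither group named in the Synopsis, Section 5 and Section 5.2.2. These passages must be reconciled with the revised SD row; which rule is right is for the sponsor to decide.

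The cost is wording in the response table, Section 9 and the continuation passages, with no new data or visits. The downside is a small departure from the adopted EBMT wording, which can be met by reporting the MR rate under the literal wording alongside.

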#### Appendix 4: New York Heart Association (NYHA)

Class	Description
I	Patients with cardiac disease but without resulting limitations of physical activity. Ordinary physical activity does not cause undue fatigue, palpitation, dyspnea, or anginal pain.
II	Patients with cardiac disease resulting in slight limitation of physical activity. They are comfortable at rest. Ordinary physical activity results in fatigue, palpitation, dyspnea, or anginal pain.
III	Patients with cardiac disease resulting in marked limitation of physical activity. They are comfortable at rest. Less than ordinary physical activity causes fatigue, palpitation, dyspnea, or anginal pain.
IV	Patients with cardiac disease resulting in inability to carry on physical activity without discomfort. Symptoms of cardiac insufficiency or of the anginal syndrome may be present event at rest. If any physical activity is undertaken, discomfort is increased.

This table is an excerpt from the Oxford Textbook of Medicine, 2nd ed. Oxford; New York: Oxford University Press, 1987, p. 222

**Appendix 5: Schedule of Assessments MM 27**

Procedures	Pre-Treatment	Cycle 1 Cycle = 28 days							Cycle 2 and beyond			Restage Every Cycle (4 weeks)	End of Study Treatment o	Follow-up	
	Baseline A	Day i,j							Day i,j					Off Study Prior to Progression P	After Disease Progression Q
		1	2	5	8	9	15	16	1	8	15				
TESTS & OBSERVATIONS															
Medical history	X						X		X D				X	X	
Physical examination	X	X					X		X D				X	X	
Vital signs, height, weight B	X	X	X	X	X	X	X	X	X	X	X		X	X	
ECOG Performance Status	X	X							X				X	X	
12-lead ECG	X	X G		X G					X H				X	X	
Chest x-ray	X														
MUGA or ECHO	X K														
Adverse event evaluation		X	X	X	X	X	X	X	X	X	X		X	X	
Concomitant medication review	X	X			X		X		X	X	X		X	X	
Survival Status															X
LABORATORY TESTS															
CBC, 3-part differential & platelets	X	X		X		X			X	X	X		X	X	
CMP C plus magnesium & phosphorus	X	X		X		X			X				X	X	
Uric acid & LDH C	X	X		X		X			X S				X S		
PT/INR F	X	X F		X F		X F			X F						
Serum or Urine β-HCG E	X														
DISEASE ASSESSMENTST															
Bone Marrow Aspiration/Biopsy L	X											X L			
Skeletal Survey N	X														
Serum free light chain	X											X M	X M	X M	
Serum immunoglobulin G, A, M	X											X	X	X	
Serum β-2 microglobulin	X														
SPEP & immunofixation	X											X	X	X	
UPEP & immunofixation	X R											X R	X R	X R	

